### **Radiologic Measurements**

Over the course of the study, participants will not be exposed to more than 0.47 mSv of radiation; we will expose participants to the lowest amount of radiation possible to achieve the aims of the research. For comparison, this total dose is less than a quarter of the exposure for a single head CT scan. Participants will be permitted to take breaks as needed.

### **Standing Long Leg X-ray**

If needed, this component will be performed at the VAPSHCS Department of Diagnostic Imaging. Participants will stand still while a frontal X-ray of the hips down is taken. This will allow us to quantify

the alignment at the hip, knee and ankle. We will also take standard foot alignment X-rays, including anterior/posterior and medial/lateral views of the feet.

We will measure the ankle alignment, if a participant is determined to have an ankle alignment type for which the study group is already full, that individual will not be able to participate further in the study, but will be compensated for the visit.

Please note, for participants that do not have a clinical diagnosis of alignment type (those with and without OA), we do not intend to inform them if we note misalignment. It is unknown at this time if ankle misalignment is causative to the development of ankle OA or if it is clinically relevant to prevention or conservative treatment of OA; these are some of the questions that this study hopes to address. Therefore, the information would not be useful to participants.

The CT scan and Biplane Fluoroscope session will be conducted in no particular order and may be conducted over multiple visits.

### CT Scan

If needed, this component may be performed at the VAPSHCS Department of Diagnostic Imaging or using the CLiMB's LineUp weightbearing CT scanner. Participants will have a CT scan taken; the scan will start at the mid-tibia (lower leg) and extend down to include the feet and ankles. For scans taken in the VAPSHCS Department of Diagnostic Imaging, participants will be seated in a small plastic frame, on the CT scanner flatbed, with both feet resting against a flat plate; the plate will apply 10% of the participants' body weight to each foot during the scan to simulate partial weight-bearing. The LineUp CT scanner is designed so that subjects can stand and naturally be weightbearing, so no frame is necessary. The CT scan will be used to generate a computational model of the subject's bony anatomy – a necessary step for generating results with the fluoroscopy system.

### Biplane Fluoroscopy – Baseline

While wearing shorts (their own or ones we provide), participants will change into standard lab shoes and enter the Biplane Fluoroscopy Laboratory. Participants will step onto an elevated walkway, which is flat, about 3-feet wide, level, and has handrails on both sides. They will be asked to walk freely up and down the walkway to get comfortable with the test environment. External markers may be placed on the shoe for tracking purposes. While participants stand still on the platform, two fluoroscopes will capture simultaneous X-ray images of the participants' foot of interest, to record the standing position of the foot bones. These dual fluoroscopes allow for tracking of the bone motion in three dimensions (3D) while participants walk. Next, participants will be asked to walk along the platform while simultaneous X-ray images of the foot of interest are taken; each X-ray exposure is expected to last about 0.5 seconds, and will image from about 3 inches above the ankle to below the bottom of the shoe or foot. This set of standing and walking trials may also be

conducted with a neutral insert in the shoes, or barefoot. With some participants, we may capture images of each foot during the standing and walking X-ray procedures.

#### Biplane Fluoroscopy – Wedged Insoles

Research staff will insert one of the wedged insole configurations (selected based on the participants' varus/valgus indication) into both of the participants' shoes. Participants in the control group may be asked to do these procedures with several different insole configurations. Participants will then repeat the standing trial, and then perform walking trials in the same format described above. With some participants, we may capture images of each foot during the standing and walking X-ray procedures. Participants will be instructed to let us know if they feel pain or discomfort during the procedures. If the shoes or inserts feel uncomfortable, we will attempt to re-fit them, if we are unable to achieve a comfortable fit, we will stop the procedures.

We will not ask participants to walk through our active fluoroscopic imaging system more than 80 times total during the entire study, and as noted above the total radiation exposure for the study will not exceed 0.47 mSv.

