### Research Design & Methodology:

Up to 120 participants with ankle OA (up to 40 with varus misalignment, up to 40 with valgus misalignment, up to 40 with neutral alignment) and up to 30 participants without ankle OA will be enrolled. Participants will be men and women, age 18-80 years, who are able to stand and walk for at least one hour without significant difficulty. Participants will undergo a series of radiological measurements including: a standard x-ray from the hips down, a set of x-rays of the legs, a CT scan from the knees down, up to 80 fluoroscopic images while walking or

standing. Participants will do the fluoroscopic trials with and without wedged shoe insoles. The radiological measurements will be used to address the aims outlined above.

At the end of this study we hope to: (1) have a better understanding of ankle arthritis, (2) be able to demonstrate the potential for an improvement upon the current clinical examination for ankle misalignment and/or OA, and (3) provide evidence for, or against, the use of shoe inserts to manage and/or treat ankle misalignment and/or OA. It is hoped that this work will aid future clinicians and researchers in delaying or preventing the onset of ankle OA in at-risk veteran and non-veteran patients.

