### **3.0 Specific Aims and Hypotheses**

Clinically, tibio-talar alignment is assessed through static weight bearing radiographs – however, stance is functionally very different than gait and the tools to capture dynamic bone motion are not readily available in clinical settings. In research, optical motion capture (a technique that uses reflective markers and infrared cameras to track position and motion) is often used to study gait, however its ability to measure dynamic bone motion and position, in this case tibio-talar alignment, is limited. Biplane fluoroscopy is a radiographic technology that can track the talus, and thus measure dynamic ankle alignment. Importantly, some neutrally aligned ankles (determined via static radiographs) may actually exhibit misalignment during gait (dynamic biplane fluoroscopy). Treatment of misaligned ankles with conservative strategies (e.g., wedged insoles) may reduce misalignment, slowing the rate of OA development. We seek to quantify dynamic ankle misalignment in OA patients, detect a possibly hidden dynamically misaligned patient population, and explore how both populations respond to a conservative treatment approach.

**Specific Aim 1:** To investigate ankle kinematics in controls and participants with OA.

**Hypothesis 1:** During gait, there are different tibio-talar kinematics between participants with OA and static varus alignment, participants with OA and static valgus alignment, and controls.

**Specific Aim 2:** To identify dynamically misaligned ankles in participants with OA who are currently classified as neutrally aligned using static analysis.

**Hypothesis 2:** Some participants with OA and static neutral alignment will exhibit varus or valgus tibio-talar misalignment when measured dynamically using biplane fluoroscopy.

**Specific Aim 3:** To evaluate the potential of lateral or medial wedging to restore alignment in participants with OA and misaligned ankles.

**Hypothesis 3:** Participants with OA and static (varus/valgus) tibio-talar misalignment will exhibit reduced misalignment when walking with (lateral/medial) wedge insoles.

**Hypothesis 4:** Participants with OA and static neutral alignment, but with dynamic (varus/valgus) tibio-talar misalignment will exhibit reduced misalignment when walking with (lateral/medial) wedge insoles.

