## **5.0 Study Procedures**

### **5.1 Study Design**

Participants in this research study will be men and women, age 18 to 80 years, who are able to walk without the assistance of an aid. People with and without ankle OA, will be enrolled. Targeted enrollment by ankle OA status and alignment type is listed in the table below. Vulnerable populations will not be specifically targeted for enrollment. See inclusion/exclusion criteria below in section 5.4.

Study Groups	Varus Misalignment	Neutral Alignment	Valgus Misalignment
up to 30 – Controls, no ankle OA	0	30	0
Up to 120 - People with Ankle OA	40	40	40

See section 5.5 below for data collection procedures and risk management.

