## **5.5 Study Visits, Data Collection, and Risk Management**

All data collection procedures will be performed at the VA Puget Sound. There are several components to the study. Participants may be asked to complete some or all components of the study depending on their eligibility, but may do so over several visits (up to 4). We anticipate that most participants will complete all study components within 3 visits over a 3-4 month timeframe, but participant schedules and the accessibility of facility resources (i.e., the ability to schedule time slots with the Dept. of Diagnostic Imaging) may extend the study timeframe beyond this estimate. We will attempt to conduct multiple components of the study during each visit in order to minimize the number of visits required for participation. Visits may last up to 5 hours each. Study visits will be scheduled by contacting the participants on phone, or during in-person contacts. We may contact participants with appointment reminders via email or phone.

During study sessions, visitors and observers will not be allowed in the lab unless the participant agrees to their presence; the participant can change her/his mind at any time.

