### **Eligibility Screening and Group Determination**

Participants will have been preliminarily screened during recruitment, then during the first visit, after informed consent is obtained, we will make a final eligibility determination. This will include verifying that the information collected during recruitment is accurate and current.

At each visit that involves exposure to radiation female participants of child-bearing potential (under age 50) will undergo a pregnancy test (urine test) so we can verify that they are not pregnant. Designated study staff will escort female participants to the bathroom and provide them with a specimen cup, pregnancy test strip, and a disposable container on which to place the used test strip. Staff will go over the test instructions, and verify the test result. Staff will not handle urine specimens, we will tell participants how to handle and dispose of the materials. If the test indicates that the participant is pregnant she will be not be able to participate in the study and we will advise her to see her regular clinical care provider. If a participant cannot continue in the study they will still be compensated for the visit.

Participants with ankle OA will be grouped based on their clinical diagnosis of ankle coronal plane alignment (varus, neutral or valgus) as noted in their medical record, and/or determined by reviewing/measuring ankle alignment in x-rays in the medical record during recruitment and screening. Participants with ankle OA who do not have a formal clinical diagnosis of alignment type, if

alignment type cannot be determined via the x-rays on file, or if there are no x-rays on file, will be categorized after undergoing the Standing Long Leg X-ray.

Participant weight and height will be measured, and his/her age, sex, race/ethnicity and Veteran status will be recorded. Participants will be asked to walk in a straight line in the hallway while a researcher times the subject to determine his/her natural walking speed.

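### Does the lack of a stated wedge-selection step for static-neutral participants put Hypothesis 4 at risk?

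*Combined protocol and SAP*

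**What the plan says.** The Abstract (Research Design & Methodology) states the general plan: "Participants will do the fluoroscopic trials with and without wedged shoe insoles". Section 5.5, Biplane Fluoroscopy – Wedged Insoles, gives the selection rule. Staff use "one of the wedged insole configurations (selected based on the participants' varus/valgus indication"), and only controls are mentioned as possibly trying several configurations.

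The OA groups are static. Under Eligibility Screening and Group Determination, participants are "grouped based on their clinical diagnosis of ankle coronal plane alignment (varus, neutral or valgus"), from records or x-rays. Section 5.1 plans "Up to 120 - People with Ankle OA", with 40 in each alignment group.

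Hypothesis 4 in section 3.0 reads: "Participants with OA and static neutral alignment, but with dynamic (varus/valgus) tibio-talar misalignment will exhibit reduced misalignment when walking with (lateral/medial) wedge insoles". Section 5.6 takes the dynamic class from the fluoroscopy trials and analyses Hypothesis 4 by the methods of Hypothesis 3.

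On timing, section 5.5 makes the CT model a prerequisite for fluoroscopy results but sets no order between CT and fluoroscopy. Participants may do "some or all components of the study depending on their eligibility, but may do so over several visits (up to 4"), and the team expects that "most participants will complete all study components within 3 visits". It also says: "We will attempt to conduct multiple components of the study during each visit in order to minimize the number of visits required for participation".

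**The concern.** A participant with static varus or valgus alignment arrives with a direction, so the wedge can be chosen at once. A static-neutral participant does not. The direction that matters for Hypothesis 4 emerges only after the baseline walking trials have been processed against a CT model, and the CT may come after the fluoroscopy session. The wish to combine components within a visit could also lead staff to run the wedge trials on the same day as the baseline.

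A static-neutral participant who later proves dynamically misaligned could then have no wedge trial in the matching direction. Analysis cannot recover a condition that was never recorded, so that participant would be lost to Hypothesis 4 unless recalled. The stake is the sample size and precision of one of the four hypotheses. If the mismatch arises from scheduling rather than from how the ankle responds to a wedge, setting such participants aside causes no bias.

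**Working it through.** **The plan's only power figure.** Section 5.6 (Power) claims more than 99% power for a 3.5 degree OA-versus-control difference. Its inputs are SDs of 1.8 and 2.9 degrees, 30 and 20 participants, 3 trials each, and a within-subject error of 1.5 degrees; a two-sided 0.05 test is assumed here.

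- Without added within-subject error: SE = sqrt(1.8²/30 + 2.9²/20) = sqrt(0.108 + 0.4205) = 0.727. Power = Φ(3.5/0.727 − 1.96) = 0.998.
- With 1.5²/3 = 0.75 added to each variance: SE = sqrt(3.99/30 + 9.16/20) = 0.769. Power = 0.995.
- 5000 simulated datasets tested on participant means gave 0.997 with pooled variance and 0.993 with unequal variances.

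The claim reproduces, but it belongs to the Hypothesis 1 contrast. The plan states no power for Hypothesis 4, so no stated figure is undermined.

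**Reach of the gap.** It covers 40/120 = 33% of OA participants, or 40/150 = 27% of everyone. Hypothesis 4 has at most 40 participants, so each one lost is at least 1/40 = 2.5% of its sample. The documents give neither the share of static-neutral ankles that are dynamically misaligned nor a rate of matching. As an assumed range, 10% to 50% misaligned gives 4 to 20 eligible participants. The number lost could be anywhere from none to all of them.

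**The provisions side by side.**

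1. The selection rule requires a varus/valgus indication. Static grouping gives none for a neutral ankle. Hypothesis 4 gives one, the dynamic class. A wedge chosen before that class is known would rest on no indication, which does not satisfy the rule.
2. Baseline trials are described before wedge trials. The freedom of order concerns CT versus fluoroscopy, not baseline versus wedge.
3. Four visits are allowed and three are expected for most participants, which leaves 4 − 3 = 1 spare. Existing CT scans may be used.
4. Section 5.5 (the additional imaging session, if needed) says that if needed images were not captured, for whatever reason, participants will be asked to return. Matching wedge images are needed for Hypothesis 4.
5. Combining components within a visit is something the team will attempt, not a rule that overrides items 1 to 4.

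**Cost of the alternatives.** Two ways of guaranteeing a match suggest themselves.

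- *Fixed order: CT, baseline, processing, then wedge on a later day.* This may use the spare visit. It also places every wedge trial in a later session than its baseline, so session and wedge effects cannot be separated in Hypothesis 4. Repeating the baseline in the later session would avoid that but needs more images.
- *Both wedge directions in every static-neutral participant.* Section 5.5 (Risks and Risk Management) estimates 0.20 mSv for 80 trials, or 0.20/80 = 0.0025 mSv each, and says some participants may need only 30. If those 30 split evenly between baseline and one wedge (assumption), a second wedge adds 15 × 0.0025 = 0.0375 mSv, and 0.0375/0.47 = 8% of the study's exposure limit. A participant already using all 80 walks has no room for it. Hypothesis 4 would not use these images in anyone who proves dynamically neutral.

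**The case for a change.** The strongest case for a change is that intention is not procedure. The wording of Hypothesis 4 settles which pairing the analysis wants, but nothing makes the dynamic class available when the insole is picked. Describing the baseline first does not require it to be processed first. The recall provision is general and not tied to dynamic classification, and the quality check after each visit is visual. Section 5.6 also does not say how a non-matching wedge trial would be handled. A few sentences would close all this, and they help only if written before the wedge trials are done.

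Much of this stands. The indication is undefined for this group, the sequence is not spelled out, and matched data are achievable rather than guaranteed. A participant who declines to return, or has used all four visits, would be lost.

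What does not stand is the step from missing detail to expected harm. Nothing in the documents points to a loss above zero. A mismatch needs a wedge chosen on no indication, followed by a recall that is not made or does not succeed. On the analysis side, Hypothesis 4 names the direction of each pairing, so an analyst would use matching trials and count the rest. A written sequence is also not free, because it brings the session problem or the added exposure shown above.

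**Conclusion.** No change to the plan follows. The gap is one of operational detail that a team testing its own Hypothesis 4 can be expected to fill. Read together, the documents point to the dynamic class as the indication for static-neutral participants, and they allow the visits and recall needed to obtain it. How to sequence the sessions is a fair trade-off between visits, radiation and separating session from wedge effects, and the documents give no figures that would settle it.

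The exposure is bounded: at most 40 participants, at least 2.5% of the Hypothesis 4 sample for each one lost, and nothing lost from Hypotheses 1 to 3. The actual loss cannot be estimated. This conclusion assumes that staff apply the selection rule as written, that recall is used when matching images are missing, and that any remaining mismatch reflects scheduling rather than response to the wedge.

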#### Wedge insole comfort

It is possible, although unlikely due to the brief nature of the data collection trials, that participants may experience discomfort or pain while standing and walking with the wedged insoles or study shoes. If this occurs it would likely be discovered immediately at the start of testing for a given wedge condition. Participants may experience mild soreness or soft tissue irritation (e.g., a blister) from walking with shoe inserts and/or in shoes that are unfamiliar, either during or shortly after the study sessions. Participants with ankle OA may experience a small increase in ankle or foot pain during or shortly after the study sessions. Participants will be instructed to inform us if they feel discomfort or pain and the procedures will be stopped so that we can adjust/re-fit the shoe/insole. If we are unable to achieve a comfortable fit the study session will be ended. Care will be taken to properly fit the shoes. Participants can take breaks at any time.

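### As described, wedge trials follow no-wedge trials and the Hypothesis 3 model has no order term, so the separate varus and valgus analyses count any mean shift between blocks as wedge effect

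*Combined protocol and SAP*

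**What the plan says.** The Abstract says only that both conditions are imaged: "Participants will do the fluoroscopic trials with and without wedged shoe insoles". The sequence appears in section 5.5.

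- **Biplane Fluoroscopy – Baseline:** "participants will change into standard lab shoes and enter the Biplane Fluoroscopy Laboratory". Before imaging, "They will be asked to walk freely up and down the walkway to get comfortable with the test environment". Standing and then walking trials follow. A neutral insert or barefoot walking may be added to this set.
- **Biplane Fluoroscopy – Wedged Insoles:** staff insert a wedge chosen by the varus or valgus indication. "Participants will then repeat the standing trial, and then perform walking trials in the same format described above". For controls the wedge trials are optional: "Participants in the control group may be asked to do these procedures with several different insole configurations".
- **Standing Long Leg X-ray:** this holds the only statement about freedom of order, "The CT scan and Biplane Fluoroscope session will be conducted in no particular order and may be conducted over multiple visits". It concerns CT against fluoroscopy, not wedge against no wedge.
- **Additional imaging session:** procedures may be repeated if images are missing or faulty. That could break the sequence for a few participants, but not by design.

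Section 5.6, Hypothesis 3, fits a linear mixed model with wedge as the fixed effect and subject and subject-by-wedge as random effects, separately for varus and valgus. The outcome is the coronal disparity from controls. Hypothesis 4 uses the same method for participants who are neutral statically but misaligned dynamically.

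**The concern.** If every participant does the no-wedge block first, wedge and block are the same variable. Anything that changes mean coronal alignment between the first and second block, such as adaptation to the lab shoes, fatigue or discomfort, enters the wedge estimate. A shift towards neutral would be read as benefit, and a shift away from neutral would hide a real benefit. The subject-by-wedge random effect does not help, because it absorbs variation between participants in the change and not a mean shift common to them.

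Hypothesis 3 is the direct test of Aim 3 for statically misaligned ankles, and the Abstract says the study will provide evidence for or against shoe inserts. That evidence would rest on an unstated assumption of no shift between blocks.

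**Working it through.** **The plan's own figure.** Section 5.6 (Power) states more than 99% power for a 3.5 degree difference, from 30 OA participants (mean -1.8, SD 1.8) and 20 controls (mean 1.7, SD 2.9), with 3 trials each and 1.5 degree within-subject error. Simulating 5000 datasets gives 99.6%, so the figure reproduces. It concerns the Hypothesis 1 comparison between groups. No power is given for the wedge contrast.

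**Identifiability.** With columns for intercept, wedge and block, the described sequence gives a design matrix of rank 2 out of 3. With both orders present the rank is 3. Adding an order term to fixed-order data therefore does nothing. A linear trial-number term can be estimated with 3 + 3 trials, but it multiplies the variance of the wedge estimate by about 4.4 and does not remove a step between blocks.

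**Direction of the shift.** Let w be the correction due to the wedge and d the block shift, with change measured on one signed coronal axis.

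- Common direction: varus change = d + w and valgus change = d - w. Half the varus-minus-valgus difference is w, free of d. If the groups respond differently, it is the average of the two wedge effects.
- Towards neutral in both groups: varus change = w + d and valgus change = -(w + d). Half the difference is w + d, so the shift remains.

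**Illustrative size in the planned separate analyses.** The 3 trials per condition and 1.5 degree error are borrowed from the Power section. The shift, the subject-by-wedge SD of the change (s = 0, 1 or 1.5 degrees) and the true benefit of 1.0 degree are assumptions. n = 40 is the maximum per group in section 5.1, and n = 30 is the OA number in the Power section.

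SE = sqrt((2 × 1.5² / 3 + s²) / n). For n = 40 and s = 1: sqrt(2.5 / 40) = 0.250. Across s, the SE is 0.194, 0.250 and 0.306 at n = 40, and 0.224, 0.289 and 0.354 at n = 30.

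Probability of declaring a benefit (noncentral t, n - 1 df, two-sided 5%, favourable direction, nominal 2.5%):

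| Net change, degrees | n = 40, s = 0 / 1 / 1.5 | n = 30, s = 0 / 1 / 1.5 |
|---|---|---|
| 0.25 | 24.2 / 16.3 / 12.2% | 19.0 / 13.1 / 10.1% |
| 0.50 | 71.2 / 49.6 / 35.7% | 58.0 / 38.8 / 27.7% |
| 0.75 | 96.5 / 83.3 / 66.6% | 90.0 / 70.9 / 53.6% |
| 1.00 | 99.9 / 97.4 / 89.0% | 99.1 / 91.7 / 78.0% |

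- No true effect and a favourable shift: the first two rows are false benefits.
- True benefit of 1.0 degree and an unfavourable shift of 0.25 or 0.5 degree: power at n = 40 falls from 89–99.9% to 67–97% or 36–71%.
- A common 0.25 degree drift that favours one group opposes the other, which at n = 40 is declared improved in at most 0.3% of studies and worse in 12–24%.

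**With remedies (simulated).** Counterbalancing 1:1 with order in the model, and no carry-over, gives 2.4–2.7% false benefit under either shift. Power for 1.0 degree stays at 89–99.9% (n = 40). The pooled signed contrast on fixed-order data, under a common-direction shift, has mean bias of about 0 and false benefit of about 2.5%.

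**The case against.** **The order is inferred.** The protocol never says that it is fixed, and staff may vary it in practice. This stands as a limit. If the order is varied, that still has to be written down, because the model ignores it.

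**A shift is speculative.** The pain statement, "Participants with ankle OA may experience a small increase in ankle or foot pain during or shortly after the study sessions", sits under the heading on insole comfort. Pain caused by the wedge is part of the wedge effect, not an order effect. The plan also has familiarisation walking, breaks and, in its words, "the brief nature of the data collection trials". All of this makes a large shift less likely; none of it makes a shift separable. The percentages above therefore cannot be read as risk estimates, and their upper ends need a subject-by-wedge SD of zero, although the model includes that term.

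**The two-group design is a partial safeguard.** A reader might infer that no analysis of fixed-order data could rescue the wedge result. The documents do not support that. The groups receive opposite wedges, so a drift in one direction cannot make both look improved, and the pooled contrast removes it. Control wedge trials might also absorb a common shift, since the outcome is disparity from controls, but they are optional and section 5.6 names no control wedge reference.

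**Baseline first protects other analyses.** The same no-wedge trials feed Hypothesis 1 and additional analysis 5, and Hypotheses 2 and 4 need the dynamic baseline before a wedge direction can be chosen. This stands and shapes the fix.

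**The aims are exploratory.** Aim 3 concerns the potential of wedging, and section 5.7 says that this is not a treatment study. That argues for a modest recommendation, not for leaving the order unaddressed.

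**Conclusion.** The point holds in a limited form. As the procedures are described, the planned separate varus and valgus analyses estimate the wedge effect plus any mean shift between blocks, whatever the direction of that shift. A common-direction shift could be removed by a pooled contrast that the plan does not include. A shift towards or away from neutral in both groups could not be removed from fixed-order OA data.

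A reader might infer that an order effect is present, or that the wedge findings will be wrong. The documents show neither: they give no size or direction for a shift, so the figures only show sensitivity under the stated assumptions. Hypotheses 1 and 2 do not use the wedge contrast and are not affected under the present sequence. This is a worthwhile, inexpensive improvement to the design rather than a fatal flaw.

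**What to change.** 1. For static varus and valgus OA participants, whose wedge direction is known from static alignment, randomise or counterbalance the order of the no-wedge and wedge blocks within alignment group. Allow a short unimaged walk after each change.
2. Record block order and visit, and add order as a fixed effect in the Hypothesis 3 model. State in section 5.6 that no wedge means the standard lab shoe.
3. Add the pooled signed contrast (half the varus-minus-valgus difference in change) as a sensitivity analysis.
4. Keep baseline first for static-neutral participants (Hypotheses 2 and 4), record their trial order and state the limitation.
5. Repeat Hypothesis 1 and additional analysis 5 in baseline-first participants, because counterbalancing puts about half of the static varus and valgus no-wedge trials second.

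**Cost.** An order list and some handling time. No added imaging is needed, so the radiation limit and the commitment to the minimum number of trials are untouched.

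**Downsides.**
- Carry-over: if 0.5 degree of wedge effect persisted into a following no-wedge block in half the participants, the benefit would be understated by 0.5 × 0.5 = 0.25 degree, and power for 1.0 degree would be 67–97% at n = 40. This errs against the wedge, and the unimaged walk reduces it without excluding it.
- Order effect elsewhere: a 0.5 degree block shift would add up to 0.5 × 0.5 = 0.25 degree to the Hypothesis 1 contrast, or 0.25 / 3.5 = 7% of the planned difference. In additional analysis 5 the compared groups would differ in order by design. The repeat in step 5 checks both.
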